3.7 Data Collection

For each patient, the following variables will be extracted from the Smart Digital Clinic electronic medical record extraction system, when possible:

- Gender and age;
- Smoking habit and alcohol consumption (units per day);
- Weight and body mass index (BMI) at the first (T0) and last visit (T1);
- Date of diagnosis of T2D;
- Date of the first visit;
- Treatment for T2D at T0 and T1;
- Levels of glycated hemoglobin (HbA1c) at T0 and T1, average HbA1c, and average fasting blood glucose;
- Creatinine clearance at T0 and T1;
- Liver enzymes at T0 and T1: alanine aminotransferase (ALT) and aspartate aminotransferase (AST);
- Lipid profile at T0 and T1: low-density lipoprotein (LDL-c) and triglycerides (TG);
- Complications of T2D;
- Treatment for the cancer;
- Family history of cancers.

The diagnosis of T2D is confirmed at diabetic centers or, in some cases, by general practitioners who refer patients to specialized diabetic centers. The accuracy of the diagnosis will be confirmed by cross-referencing with the Piedmont Diabetic Registry (PDR) and involving a second person to ensure precise assessment.

Glycated hemoglobin will be considered high if its values exceed or equal 8%, indicating glycemic decompensation, while it will be considered low if it presents values below 8%.

BMI categories will be divided into underweight (BMI <18.5 kg/m²), normal weight (BMI 18.5 – 25 kg/m²), and overweight (BMI >25 kg/m²).

Regarding the treatment of T2D, participants will be categorized and grouped for statistical purposes into the following classes:

- Dietary therapy;
- Metformin/Acarbose;
- Sulfonylurea;
- Metformin + GLP1/DPP4 inhibitors (DPP4i) or only GLP1 or only DPP4i;
- Metformin + SGLT2 inhibitors (SGLT2i) or only SGLT2i;
- Basal insulin + GLP1/DPP4i +/- Metformin;
- Basal insulin +/- Metformin +/- SGLT2i;
- Basal bolus insulin;
- Basal bolus insulin +/- Metformin +/- SGLT2i.

Furthermore, complications of metabolic pathology will be extracted from the dedicated section of the program, where they are systematically recorded and organized, and their diagnosis is conducted in accordance with appropriate guidelines. These complications will be divided into the following categories: vasculopathy, neuropathy, hypertension, heart disease, renal failure, and retinopathy.

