Finally, regarding cancer, treatment will be categorized into three classes: chemotherapy, surgery, and radiotherapy. Additionally, cancer types will be divided to ensure greater homogeneity among groups, including the nervous system, head and neck, thorax, gastrointestinal, gynecological, urinary tract, male genital system, skin, blood, breast, soft tissues, endocrine glands, and neuroendocrine cancers.

Such information will be collected at the diabetes diagnosis visit and the last visit before cancer onset for subjects experiencing the event, and at the last available visit for the remaining subjects.

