3.8 Sample Size

Assuming a type I error of 0.05, a power of 80%, a prevalence of subjects with high glycated hemoglobin levels of 13%, and a correlation between covariates in the model of 0.1, it will be necessary to identify 779 cancer cases to highlight a Hazard ratio of 1.2 for the association between glycated hemoglobin and cancer onset.

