3.9 Statistical Analysis

Descriptive statistics will be calculated to summarize patient information.

Categorical variables will be reported as absolute frequencies and percentages, while numerical variables will be reported as mean and standard deviation or median (Q1-Q3) if not distributed according to a normal random variable according to the Shapiro-Wilk test and observation of the QQ plot.

SCDU di Endocrinologia

AOU Maggiore della Carità, [name]
[contact] (Reparto); [contact]
[contact]

Univariate and multivariate Cox proportional hazards regression models will be used to estimate hazard ratios (HRs) and corresponding 95% confidence intervals (95% CI) for the association between some risk factors, including particularly glycemic level, and cancer onset. The stepwise method will be used to select variables to include in the model. For this analysis, time to event will be calculated as the number of years between cancer onset and diabetes diagnosis for subjects who develop the cancer, and as the number of years between the last available visit and the date of diabetes diagnosis. The possibility of conducting an analysis separately for cancer type or considering specific cancer types based on the number of observed events will be evaluated. The same models will be used to estimate the association with the risk of recurrence, second cancer, or both in patients who have developed cancer. In this case, time to event will be calculated considering the difference in years between recurrence onset, second cancer, or last visit and the onset of the first cancer.

Linear regression models will be used to evaluate the relationship between variables measured at diagnosis and time to cancer onset. In case the assumptions of the linear model are not met (normality of residuals and homoscedasticity), the Spearman correlation coefficient will be calculated to measure the correlation between numerical variables and time to tumor onset, while the Mann-Whitney or Kruskall-Wallis tests will be used when variables measured at baseline are categorical.

The significance level will be set at 0.05, and all tests performed will be two-tailed. Finally, the analyses will be conducted using SAS software (version 9.4; SAS Institute, Cary, NC, USA).

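### The Cox model for cancer onset starts at diabetes diagnosis, but the plan neither names the HbA1c exposure nor limits fixed covariates and stepwise candidates to values known at that time

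*Combined protocol and SAP*

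**What the plan says.** Sections 3.6 and 3.9 start both follow-up and Cox time at the diagnosis of T2D. Section 3.9 says that the Cox models are "for the association between some risk factors, including particularly glycemic level, and cancer onset", and that "The stepwise method will be used to select variables to include in the model". It gives no candidate list and no rule on when a covariate must have been measured. The next paragraph does have such a rule, but for a different model: "Linear regression models will be used to evaluate the relationship between variables measured at diagnosis and time to cancer onset".

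Section 3.7 collects "Levels of glycated hemoglobin (HbA1c) at T0 and T1, average HbA1c, and average fasting blood glucose" and "Treatment for T2D at T0 and T1". It adds that "complications of metabolic pathology will be extracted from the dedicated section of the program", with no onset date and no restriction to diagnosis. The averages have no stated window. The later measurement is taken at "the last visit before cancer onset for subjects experiencing the event, and at the last available visit for the remaining subjects".

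The 8% cut-off in section 3.7 is tied to none of the HbA1c versions. Nor is the sample-size input in section 3.8, "a prevalence of subjects with high glycated hemoglobin levels of 13" (per cent). Time-dependent covariates, a landmark and a lag are not mentioned anywhere.

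Section 3.7 defines T0 as the first visit. It collects that date separately from the diagnosis date and notes that some diagnoses are made by general practitioners who then refer. Section 3.3 (first diagnosis at the clinic) and the end of section 3.7 (a diagnosis visit) suggest that the two dates coincide, but the plan does not say so.

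**The concern.** A Cox model compares, at each event time, the patient who has the event with everyone still at risk. A covariate held fixed from time zero must therefore be known at time zero. A complication recorded in year 15, used as a fixed covariate, is credited to that patient from year 0. Yet the patient had to stay cancer-free and under observation for 15 years to acquire it. The later visit in this plan also falls at a time set by cancer onset or the end of follow-up, so its timing depends on the outcome being modelled. Taking it before cancer in cases avoids post-cancer values but does not remove this problem.

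The stake is the primary objective, identifying risk factors for cancer onset, with glycaemia as the lead exposure. The bias does not shrink with more events. Leaving three HbA1c versions open also allows the version to be chosen after results are seen.

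**Working it through.** **1. The plan's own figure.** Section 3.8 states 779 events for HR 1.2, two-sided 0.05, 80% power and 13% exposed. The standard formula is events = (1.960 + 0.842)² / [p(1−p) · (ln HR)²] = 7.849 / (0.1131 × 0.03324) = 2,088. With R² = 0.1 it gives 2,320. A value near 779 appears only if √0.1131 = 0.336 replaces 0.1131, with R² = 0.1 (780). That is a separate matter and nothing below relies on it. What matters here is that p enters through p(1−p), so the event number depends on which HbA1c the 13% describes (step 4).

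**2. States that begin or end during follow-up (no true effect).** The documents give no rates. Assumed: cancer h = 1.5%/yr, loss or death c = 4%/yr, so a = h + c = 5.5%/yr, and onset of the state at λ per year.

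- Patients without the state by the end of follow-up: mean follow-up 1/(a+λ).
- Patients with it: 1/(a+λ) until onset, then 1/a more.
- The share ending in cancer is h/a in both groups.
- Apparent rate ratio = [1/(a+λ)] / [1/(a+λ) + 1/a] = a/(2a+λ). It tends to 0.5 even for a rare state.
- For a class that everyone starts in and leaves at rate λ, the ratio for still being in it is the inverse, 2 + λ/a.

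| λ per year | Present by T1: formula | Cox, simulated | Cox, 15% at diagnosis | Still in initial class: formula | Cox, simulated |
|---|---|---|---|---|---|
| 1% | 0.055/0.12 = 0.46 | 0.45–0.47 | 0.69 | 2.18 | 2.1 |
| 2% | 0.055/0.13 = 0.42 | 0.42–0.44 | 0.58 | 2.36 | 2.3 |
| 4% | 0.055/0.15 = 0.37 | 0.37–0.39 | 0.45 | 2.73 | 2.6–2.7 |

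The simulations add diagnosis in 1990–2010 and an assumed closure in 2024, giving about 790 events. With cancer at 1–2%/yr and loss at 2–8%/yr, the range at 1–4%/yr is 0.36–0.45. Coded as present at diagnosis the HR is 0.99–1.00; time-updated, 0.99–1.01.

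**3. HbA1c of 8% or more as a fixed covariate (no true effect).** Same rates; assumed mean 6.9 and SD 0.98 at diagnosis (13% high), within-person SD 0.5, annual visits, equal slopes, n = 4,020, 500 replicates.

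| Mean drift, points/yr | −0.05 | −0.02 | 0 | +0.02 | +0.05 |
|---|---|---|---|---|---|
| HR, T1 | 2.56 | 1.46 | 1.00 | 0.71 | 0.46 |
| HR, average | 1.91 | 1.34 | 1.06 | 0.85 | 0.64 |

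T0 HbA1c gives 1.00 and time-updated HbA1c 0.99–1.00. With zero mean drift but slope SD 0.02 or 0.05, T1 gives 0.90 or 0.72. A second set of assumptions (slope SD 0.03, censoring uniform over 5–30 years) gives T1 1.32, 0.87 and 0.62 at drift −0.03, 0 and +0.03. The figures therefore depend on the model. For scale, ln 1.46 = +0.38 and ln 0.71 = −0.34, against ln 1.2 = 0.18 for the planned effect.

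**4. Effect on section 3.8.** If 13% are high at T0, the share high at T1 is 9% at drift −0.02 and 20% at +0.02. Required events scale as 1/[p(1−p)]: 0.1131/0.0819 = 1.38 times, or 0.1131/0.16 = 0.71 times, the number at 13%.

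**5. Stepwise selection.** Assumed: seven candidates (HbA1c at T0, T1 and average; one complication and one treatment state, each at diagnosis and by T1), entry and removal at p = 0.05, no true effects. The two states coded by T1 were selected in 100% of runs. T1 or average HbA1c was selected in 84, 16 and 94% at drift −0.02, 0 and +0.02. With only the three time-zero candidates, T0 HbA1c was selected in 5–6%.

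**The case against.** The strongest reply is that the plan never says T1 values, averages or later complications will enter the Cox model. Enrolment at first diagnosis, a diagnosis visit, and a secondary objective describing patients at diagnosis all fit a model using diagnosis values only. That stands. A reader might infer that the plan prescribes a biased primary analysis; the documents support only that it leaves one open.

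A reader might also infer that every later-measured treatment will look protective. That fails. Section 3.7 records the regimen at the visit, in nine classes. Classes started later and kept look protective, while classes that patients leave look harmful, so the direction depends on the class and the reference.

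Nor do the documents support a particular direction for HbA1c. They give no drift, slope variation, cancer incidence, loss rate or closure date, and reasonable assumptions put the zero-drift average on either side of 1 (1.06 or 0.94). It also cannot be assumed that the averages span all of follow-up, because no window is given. The stepwise candidate list was constructed and omits age, gender, smoking and BMI. It shows only that stepwise selection does not screen out mistimed variables.

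None of this supplies the missing rule. The linear model has a timing restriction and the Cox model does not.

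**Conclusion.** The concern holds as an omission that permits a biased primary analysis. It should be closed before analysis. Confidence is high that the rule is missing and that bias is possible, but not in any single size.

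Under the assumed rates and no true effect, a complication, or a treatment started later and kept, gives HR about 0.4 to 0.5 at 1–4%/yr, or 0.45 to 0.7 if 15% have it at diagnosis. A treatment class that patients leave gives about 2.1 to 2.6. Neither result needs any HbA1c drift.

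For T1 or average HbA1c, direction and size are unknown from the documents. The bias may be close to nil with no drift and equal slopes, but it can exceed the planned effect at a drift of 0.02 points per year.

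**What to change.** In section 3.9:

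1. Name one HbA1c measurement as the primary exposure. State whether the question is HbA1c at diagnosis or current HbA1c (the investigators' choice), and tie the 13% in section 3.8 to that measurement.
2. Define T0 relative to the diagnosis date. Where the first visit is later than diagnosis, start risk time at that visit (delayed entry). Otherwise T0 values would themselves post-date time zero.
3. Allow as fixed covariates and stepwise candidates only values known at the start of risk time.
4. Enter later HbA1c (the average as a running mean), treatment and complications only as dated time-updated covariates, or in a landmark or follow-up-matched analysis. Otherwise report T1 values and averages descriptively.

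Item 1 and the candidate rule are changes of wording. The rest has real costs. Establishing complications at diagnosis, or time-updated values, needs dated records, which may not exist for all patients: section 3.7 collects variables only where possible, and section 3.6 records cancer onset by year, so ordering within the onset year is coarse. A T0 model also answers a different and probably weaker question. In the same simulations a true HR of 1.2 for current HbA1c appears as 1.07–1.12 with T0, 1.12–1.15 with a running mean, and 1.19–1.21 with time-updated HbA1c.

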3.8 Sample Size

Assuming a type I error of 0.05, a power of 80%, a prevalence of subjects with high glycated hemoglobin levels of 13%, and a correlation between covariates in the model of 0.1, it will be necessary to identify 779 cancer cases to highlight a Hazard ratio of 1.2 for the association between glycated hemoglobin and cancer onset.

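### The 779 cancer cases in section 3.8 give about 40% power at HR 1.2, not 80%; the stated inputs require about 2,109 cases

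*Combined protocol and SAP*

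**What the plan says.** Section 3.8 (Sample Size) sizes the study on one association, that of HbA1c with cancer onset. It takes a type I error of 0.05, 80% power, "a prevalence of subjects with high glycated hemoglobin levels of 13%, and a correlation between covariates in the model of 0.1", and concludes that "it will be necessary to identify 779 cancer cases to highlight a Hazard ratio of 1.2". It names no formula or software and mentions no other hazard ratio.

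Two other sections supply the remaining inputs. Section 3.7 (Data Collection) makes the exposure binary: "Glycated hemoglobin will be considered high if its values exceed or equal 8%, indicating glycemic decompensation", with anything below that classed as low. Section 3.9 (Statistical Analysis) specifies Cox proportional hazards models and adds: "The significance level will be set at 0.05, and all tests performed will be two-tailed".

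**The concern.** A binary exposure carried by only 13% of patients gives little information per event, and HR 1.2 is a small effect. Fewer than 800 events looks far too few for 80% power under those conditions.

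This is the only quantitative planning statement in the document, and it concerns the risk factor that section 3.9 singles out. A reader who sees 779 cases reached would conclude that the study was adequately powered for HR 1.2. If the figure is wrong, a non-significant HbA1c result would carry much less weight than the plan implies. Section 3.9 also selects variables stepwise, so an underpowered HbA1c term could drop out of the final model.

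**Working it through.** **Inputs**

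- Two-sided alpha 0.05 (sections 3.8 and 3.9): z = 1.95996
- Power 80% (section 3.8): z = 0.84162
- Binary exposure (section 3.7) with prevalence p = 0.13 (section 3.8): variance p(1 − p) = 0.13 × 0.87 = 0.1131
- HR 1.2 (section 3.8): ln 1.2 = 0.1823, squared 0.03324
- Correlation 0.1 (section 3.8): R² = 0.01 if it is a correlation, R² = 0.1 if it was meant as R-squared

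**Formula** (Schoenfeld, with the Hsieh–Lavori adjustment for covariates)

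D = (z_alpha + z_power)² / [p(1 − p) × (ln HR)² × (1 − R²)]

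The numerator is (1.95996 + 0.84162)² = 7.849.

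**Attempt to reproduce 779 at HR 1.2**

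- R² = 0.01: 7.849 / (0.1131 × 0.03324 × 0.99) = 2,108.8, so 2,109 cases
- R² = 0.1: 2,319.7, so 2,320 cases
- No adjustment: 2,087.7, so 2,088 cases

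The ratios to the stated figure are 2,109 / 779 = 2.7 and 2,320 / 779 = 3.0.

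**Other readings at HR 1.2**

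- One-sided alpha, which section 3.9 rules out: 1,661.1, so 1,662 cases (R² = 0.01). One-sided power with 779 cases is about 52%.
- Freedman's formula with unequal groups: about 1,826 to 2,391 cases, depending on which group is taken as exposed.
- Prevalence taken among the cases instead of the cohort: about 1,850 cases.
- Any other prevalence: without covariate adjustment, 779 cases would need a variance of 7.849 / (779 × 0.03324) = 0.303. A binary variable cannot exceed 0.25. At p = 0.5 the requirement is 944.5, so 945 cases, and 779 would give about 72% power.

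**What 779 cases deliver** (p = 0.13, R² = 0.01)

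- SE of the log hazard ratio = 1 / √(779 × 0.1131 × 0.99) = 0.1071
- Power at HR 1.2 = Φ(0.1823 / 0.1071 − 1.96) = 39.9% (36.8% if R² = 0.1)
- HR detectable with 80% power = exp(2.8016 × 0.1071) = 1.35 (1.37 if R² = 0.1)
- An estimate exactly equal to 1.2 would have a 95% CI of exp(0.1823 ± 1.96 × 0.1071), about 0.97 to 1.48, and would not be significant.

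**Where 779 may come from**

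Keeping every other input (R² = 0.01) and changing only the hazard ratio:

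| HR | Cases required |
|---|---|
| 1.34 | 819 |
| 1.35 | 778.3, so 779 |
| 1.36 | 742 |

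Entering a log hazard ratio of 0.30 directly gives 778.9, also 779.

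**The case against.** The strongest objection concerns the cause. The document mentions no HR other than 1.2, so HR 1.35 is an inference, and its match to 779 depends on R² = 0.01. With R² = 0.1, HR 1.35 would need 856.2 cases. A rival account keeps HR 1.2: if the standard deviation √0.1131 = 0.336 is put where the variance belongs and R² = 0.1, the result is 780.1, or 779.2 with the z-values rounded to 1.96 + 0.84 = 2.80. That formula is invalid and does not defend 779, but it shows that the slip could lie in the variance instead of the hazard ratio. This point stands: HR 1.35 is the likely origin, not an established one.

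A second objection is that 779 is a stated requirement and not a forecast. Section 3.3 fixes the cohort as patients first diagnosed between 1990 and 2010, but the document gives neither its size nor the expected number of cancers. This also stands, and it means the detectable effect should be restated for the number of cases actually found.

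Third, the study is a retrospective record review without intervention. The error changes no eligibility rule, data item or model. No passage says that a null result will be taken to exclude an effect, and the planned confidence intervals would show the imprecision. That limits the harm to how power and a non-significant result are described. It does not make the stated power correct.

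Reading HR 1.2 as an effect per unit of continuous HbA1c does not help: the calculation uses a prevalence and gives no standard deviation for HbA1c.

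**Conclusion.** The concern holds. At HR 1.2 the plan's own inputs require about 2,109 cases (2,320 if 0.1 is R²), and 779 cases give 37% to 40% power. If the true hazard ratio is 1.2, the HbA1c test would miss it about 60% of the time. The effect that 779 cases can detect with 80% power is HR 1.35 to 1.37.

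These figures assume a fixed binary exposure, proportional hazards and the stated 13% prevalence, and they ignore stepwise selection. The conclusion does not depend on how the 0.1 is read, or on the prevalence, since no binary exposure makes 779 enough at HR 1.2 with the stated error rates. Only the explanation of how 779 arose remains uncertain. Because the case count and the power claim contradict each other, section 3.8 must be corrected.

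**What to change.** Rewrite section 3.8 so that its figures agree:

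1. Name the formula or software, and say whether 0.1 is a correlation or an R².
2. Choose one of two consistent statements. Either 779 cases give 80% power for HR 1.35 and about 40% for HR 1.2 (1.37 and 37% if 0.1 is R²), or HR 1.2 is kept and about 2,109 cases are required (2,320 if 0.1 is R²). As eligibility is fixed by calendar period, the first is the practical choice unless the cohort yields far more cases.
3. Once the number of cases D is known, report the hazard ratio detectable with 80% power: exp(2.8016 / √(D × 0.1131 × (1 − R²))), replacing 0.1131 with the variance at the observed prevalence.
4. State in section 3.9 that a non-significant HbA1c result will not be taken as evidence against HR 1.2, and that interpretation will rest on the confidence interval.

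The cost is a few sentences and a less favourable stated detectable effect. The first option needs no extra patients, data or analyses.

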3.9 Statistical Analysis

Descriptive statistics will be calculated to summarize patient information.

Categorical variables will be reported as absolute frequencies and percentages, while numerical variables will be reported as mean and standard deviation or median (Q1-Q3) if not distributed according to a normal random variable according to the Shapiro-Wilk test and observation of the QQ plot.

SCDU di Endocrinologia

AOU Maggiore della Carità, [name]
[contact] (Reparto); [contact]
[contact]

Univariate and multivariate Cox proportional hazards regression models will be used to estimate hazard ratios (HRs) and corresponding 95% confidence intervals (95% CI) for the association between some risk factors, including particularly glycemic level, and cancer onset. The stepwise method will be used to select variables to include in the model. For this analysis, time to event will be calculated as the number of years between cancer onset and diabetes diagnosis for subjects who develop the cancer, and as the number of years between the last available visit and the date of diabetes diagnosis. The possibility of conducting an analysis separately for cancer type or considering specific cancer types based on the number of observed events will be evaluated. The same models will be used to estimate the association with the risk of recurrence, second cancer, or both in patients who have developed cancer. In this case, time to event will be calculated considering the difference in years between recurrence onset, second cancer, or last visit and the onset of the first cancer.

Linear regression models will be used to evaluate the relationship between variables measured at diagnosis and time to cancer onset. In case the assumptions of the linear model are not met (normality of residuals and homoscedasticity), the Spearman correlation coefficient will be calculated to measure the correlation between numerical variables and time to tumor onset, while the Mann-Whitney or Kruskall-Wallis tests will be used when variables measured at baseline are categorical.

The significance level will be set at 0.05, and all tests performed will be two-tailed. Finally, the analyses will be conducted using SAS software (version 9.4; SAS Institute, Cary, NC, USA).

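### Stepwise selection exempts no variable, so the adjusted HbA1c hazard ratio that section 3.8 sizes may go unreported or be reported because it was significant; its time point is also open

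*Combined protocol and SAP*

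**What the plan says.** Section 3.9 plans univariate and multivariable Cox models for the association between "some risk factors, including particularly glycemic level, and cancer onset". On building the multivariable model it says "The stepwise method will be used to select variables to include in the model". It gives no list of candidates, no entry or stay level specific to selection, and no variable that stays in regardless. The only significance level it states is a general 0.05, two-sided. The same models are reused for recurrence and second cancer.

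Section 3.8 sizes the study on one exposure, high HbA1c, at 13% prevalence. It assumes "a correlation between covariates in the model of 0.1" and concludes that "it will be necessary to identify 779 cancer cases to highlight a Hazard ratio of 1.2".

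Section 3.7 collects "Levels of glycated hemoglobin (HbA1c) at T0 and T1, average HbA1c, and average fasting blood glucose". It sets the split, in percent, as "Glycated hemoglobin will be considered high if its values exceed or equal 8". Besides the diabetes diagnosis visit, values are taken at "the last visit before cancer onset for subjects experiencing the event, and at the last available visit for the remaining subjects".

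**The concern.** An allowance for correlation among covariates has a purpose only for an adjusted estimate, so the quantity that section 3.8 sizes is the adjusted HbA1c HR. A selection rule that protects no term can remove that estimate from the final model. If it stays only because it passed a significance test, it is on average too far from 1. Confounders such as smoking can be dropped by the same rule.

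The time point is a second gap. T0, T1 and average HbA1c are different exposures, and T1 and the average are known only at the end of follow-up. Section 3.9 ties the linear models to values at diagnosis but does not do so for the Cox models. The choice could therefore be made after the results are seen.

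**Working it through.** **Inputs.** From section 3.8: HR 1.2, prevalence 0.13, power 80%, type I error 0.05, correlation 0.1, 779 events. From section 3.9: two-sided tests. Assumed: a stay level of 0.05 to 0.15, and selection approximated by the Wald test on HbA1c alone.

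**The plan's own figure.** The events formula for a binary covariate in a Cox model is D = (z₁ + z₂)² / [p(1−p) · (ln HR)² · (1−R²)].

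- Here p(1−p) = 0.13 × 0.87 = 0.1131 and ln 1.2 = 0.1823.
- Reading 0.1 as a correlation (R² = 0.01): D = (1.960 + 0.8416)² / (0.1131 × 0.1823² × 0.99) = 2,109.
- Reading 0.1 as R²: D = 2,320.
- The stated 779 is not reproduced at HR 1.2. It does match HR 1.35 with R² = 0.01 (778.3, rounded up). That is a separate matter, so the check below uses 2,109 events, where power really is 80%.

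**How often HbA1c is dropped.**

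- SE = 1/√(2,109 × 0.1131 × 0.99) = 0.0651, so δ = 0.1823/0.0651 = 2.80.
- P(kept) = Φ(δ − c) + Φ(−δ − c), where c is the critical value of the stay level.
- Mean log HR if kept = 0.1823 + SE × [φ(c − δ) − φ(c + δ)] / P(kept).

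| Stay level | c | Dropped | Mean log HR if kept | HR if kept | CI non-coverage if kept |
|---|---|---|---|---|---|
| 0.05 | 1.960 | 20.0% | 0.2051 | 1.228 | 3.1% |
| 0.10 | 1.645 | 12.4% | 0.1975 | 1.218 | 2.9% |
| 0.15 | 1.440 | 8.7% | 0.1936 | 1.214 | 2.7% |

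The log HR is about 12% too large at 0.05 (0.2051/0.1823 = 1.125) and 6% too large at 0.15. Non-coverage of the nominal 95% interval stays below 5%.

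**Losing one weak confounder.** Assume 30% prevalence, correlation 0.1 with high HbA1c, and confounder HR 1.15.

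- Covariance = 0.1 × √(0.1131 × 0.21) = 0.0154.
- Confounder prevalence is 0.30 + 0.0154/0.13 = 41.9% with high HbA1c and 0.30 − 0.0154/0.87 = 28.2% with low.
- Bias ratio = (1 + 0.419 × 0.15)/(1 + 0.282 × 0.15) = 1.020, so HR 1.20 becomes 1.22.
- At 2,109 events and a 0.05 stay level it is dropped 16.7% of the time. The average shift is about 0.167 × 2.0% = 0.3%.
- A confounder with HR 1.3 would move 1.20 to 1.25 if lost, but is dropped less than 0.1% of the time.

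**Time point.** Section 3.7 gives three HbA1c measures, and neither section 3.8 nor 3.9 picks one for the Cox model. T0 itself needs a definition: the variable list in section 3.7 calls it the first visit, the end of that section refers to the visit at diabetes diagnosis, and the two dates are collected separately.

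**The case against.** The strongest reply is that section 3.9 names glycemic level first and mentions stepwise afterwards, so stepwise may be meant only to choose the covariates around it. The text does not settle this. A reader might infer that the plan intends to put HbA1c through selection; the documents support only the weaker statement that nothing exempts it.

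Second, the primary objective in section 2 is broad, to identify risk factors, and selection suits that aim. This stands for the other candidates. It does not explain why the exposure that sizes the study should depend on selection for its adjusted estimate.

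Third, the form of HbA1c and the selection level are arguably given. The form is: section 3.7 defines the split and section 3.8 uses the prevalence of the high class. The general 0.05 may also be meant to govern selection. Only the time point is wholly open.

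Fourth, the harm is small. The 20% dropped is one minus the power, and a forced term would be non-significant just as often. That is correct. The difference is that a forced estimate and its interval are always reported, free of selection. The univariate HR would appear in any case, but it is crude and is not the quantity sized.

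**Conclusion.** The point holds as a modest but cheaply corrected weakness. Under the plan as written, the adjusted HbA1c HR is not certain to be reported, and its time point is not fixed. At HR 1.2 with true 80% power, it would be missing 20% to 9% of the time and average 1.23 to 1.21 when kept. These figures rest on the assumed stay levels and on a normal approximation that ignores competition among covariates.

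Three stronger readings should be resisted. Confidence intervals are not shown to fail: non-coverage stays below 5% in the calculation above. Confounding from dropped covariates is not shown to be serious: losing one weak confounder moves the HR by about 2%. Finally, a reader might apply the calculation to the stated 779 events, where power at HR 1.2 is about 40% and HbA1c would be dropped about 60% of the time at 0.05. Most of that comes from the mismatch between 779 events and HR 1.2, which is a sample-size problem. If 779 belongs to HR 1.35, the drop rate at 0.05 is again 20%.

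**What to change.** In section 3.9, pre-specify one primary Cox model that forces in HbA1c at T0 (8% or above versus below), age at diagnosis, sex, smoking and BMI at T0. Report the HbA1c HR and its confidence interval whatever its significance. T0 is preferred because T1 and average values are known only at the end of follow-up. Define T0 as the diabetes diagnosis visit, and confirm that the 13% in section 3.8 is the prevalence at T0, or restate it.

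Keep stepwise as a labelled exploratory step with stated entry and stay levels, able to add other collected variables but not to remove forced ones. In the adjusted recurrence and second-cancer models, always keep HbA1c, with a shorter forced list because only patients who have had cancer contribute.

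The cost is a few sentences and a slightly longer model; every forced variable is already on the collection list. A rule for missing values in the forced terms is also needed, since the variables "will be extracted from the Smart Digital Clinic electronic medical record extraction system, when possible".
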